## 5.3 Post-treatment evaluation

Four weeks after the last of the 3 treatment sessions or follow-up visits (day 84 +/- 7 days) subjects will be asked about any side effects, reactions or adverse events that have occurred since the last visit. In the treatment arm, a dermatologist will then evaluate for any gross residual lesion as per protocol defined response criteria (see section 9.0) and a deep excisional biopsy encompassing entire region will be performed. Biopsy specimen will be evaluated for histopathologic clearance of tumor. If tumor cells are present, standard of care will be performed. In the control arm, biopsy specimen will be evaluated for histopathologic clearance of tumor and after gross evaluation and measurement of lesion by a dermatologist, standard of care will be performed.

## 5.4 Early discontinuation of therapy

Grading for adverse events as determined by US Department of Health Common Terminology Criteria for Adverse Events (CTCAE version 4.0)

Any subject with a non-laboratory Grade III or higher toxicity that is possibly, probably or definitely related to involvement in our study will be considered for removal.

## **6.0 DOSING DELAYS/DOSE MODIFICATIONS**

### **6.1 Study Agent**

There are no expected dosing delays or dosing modifications for this study. Due to the fact we are testing specific laser parameters for the potential efficacy of clearing certain types of basal cell carcinomas, we will not be adjusting the settings.

However, should the subject experience any adverse effects secondary to the use of the multiplex laser, they will immediately be provided with supportive care tailored to the nature of the adverse effect (see section 4.2). In addition, there are no expected systemic toxicities. If the expected and unexpected effects are not tolerable, the subject may also withdraw from the study at any point.

In our study, early termination will be based on presence of intolerable side effects and desire to withdraw from studies. Should our treatment prove ineffective, all patients will receive standard treatment of care immediately.

### **6.2 Other Agent(s)**

N/A

## **7.0 AGENT FORMULATION AND PROCUREMENT**

### **7.1 Agent**

#### **7.1.1 Other names**

CYNERGY VASCULAR WORKSTATION

#### **7.1.2 Classification**

Dual wavelength 595 nm / 1064 nm laser

#### 7.1.3 Mode of action

Selective photothermolysis

#### 7.1.4 Storage and stability

N/A

#### 7.1.5. Dose specifics

595 nm:

Fluence = 10 J/cm^2

Pulse duration = 10 ms

Spot size = 10 mm

Interpulse delay: 500 ms

1064 nm:

Fluence = 40 J/cm^2

Pulse duration = 10 ms

Spot size = 10 mm

10% overlap with a single pass, along with 4 mm of normal skin.

Dynamic cooling.

#### 7.1.6 Preparation

N/A

#### 7.1.7 Administration

Single pass of 595 nm wavelength followed by a single pass of 1064 nm wavelength. Administration of wavelengths separated by a 500 ms delay. Each pass is composed of pulses of laser that will have 10% overlap between pulses. Treated area will include a 4 mm margin of normal skin. Dynamic cooling feature will be provided.

#### 7.1.8 Incompatibilities

There are no direct incompatibilities, however, contraindications have been included in exclusion criteria.

#### 7.1.9 Availability

In office

#### 7.1.10 Side effects

- Pain of the skin
- Edema
- Erythema and/or purpura
- Temporary hypo- or hyperpigmentation

#### 7.1.11 Nursing implications

None

#### 7.1.12 Reported Adverse Events and Potential Risks

Likely:

- Pain of the skin
- Edema
- Erythema and/or purpura
- Temporary skin hypopigmentation or hyperpigmentation

Unlikely:

- Hematoma
- Scarring
- Herpes Simplex Virus outbreak if treating an area with past recurrent outbreaks, usually around the mouth
- Skin infection
- Skin ulceration/ bullous dermatitis

### 8.0 CORRELATIVE/SPECIAL STUDIES(*if applicable to this study*)

N/A

## 9.0 MEASUREMENT OF EFFECT

### 9.1 Guidelines for Evaluation of Measurable Disease

We will measure disease both clinically and histologically. Clinically, a dermatologist will visually inspect for the lesion and measure the size of any residual tumor with perpendicular diameters ( $d_1$  and  $d_2$ ). Surface area (SA) will be calculated as that for an ellipse, by  $SA = \pi r_1 r_2$ , where  $r_1 = d_1/2$  and  $r_2 = d_2/2$ . Residual tumor burden will be calculated by change in surface area of the lesion. Histologically, an excisional biopsy will be performed in order to examine for any residual tumor cells in the lesion. We will classify response according to our criteria below.

### 9.2 Response Criteria

For determination of response, we will consider:

- Complete response (CR):

- 1) Both clinical and histological disappearance of the target lesion or
- 2) Positive clinical assessment of the "lesion" but negative histology.

- Partial response (PR):

- 1) At least 10% decrease in the size of lesion on clinical evaluation and positive histology or
- 2) Complete clinical clearance of the lesion and positive histology.

- Progression of disease : At least 10% increase in the size of the lesion on clinical evaluation.

- Stable disease (SD): Clinically, neither sufficient reduction to qualify for PR nor sufficient increase to qualify for PD.

The following table summarizes the above response criteria.

		Clinical assessment			
Histology		No lesion	Lesion ≤90% baseline size	Lesion >90 but <110% baseline size	Lesion ≥110% baseline size
	Positive	PR	PR	SD	PD
	negative	CR	CR	SD*	PD*

\* not expected to occur.

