### **2.1 Primary objectives**

The primary objective of the study is to preliminarily assess the efficacy of the 595/1064 nm multiplex laser for the treatment of superficial and nodular basal cell carcinomas less than 1.5 cm in size.

Efficacy will be measured both clinically and histologically. This will first be determined by clinical dermatologic evaluation for the gross appearance of residual lesion. Residual tumor burden will be calculated by change in surface area of the lesion. Histological clearance will be determined by absence of residual tumor cells on histopathology of biopsy following treatment. The primary endpoint is response, defined as CR or PR. (see Section 9).

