## 4.2 Supportive Care Guidelines

The 595/1064 nm multiplex laser has a cooling feature (Smart cool 6-air cooling system) available for patient comfort during laser sessions. If the subject is concerned about being uncomfortable during the laser treatment session, an additional topical anesthetic may be applied before each treatment.

After treatment, should the subject experience any expected or unexpected adverse side effects, supportive care will be offered. These include:

- Skin pain: The subject may experience discomfort during and immediately after laser treatment. This typically resolves within 24-48 hours. Administration of topical and/or oral pain care will be determined on a case-by-case basis.
- Skin ulceration or bullous dermatitis: The laser may cause slight cutaneous disruption that can take several days to heal. The disruption may lead to mild swelling or crusting that may remain photosensitive for 2-12 weeks following treatment. Subjects will be informed of the potential risk and will be advised to wear sunscreen before and after treatment. Any blistering or crusting that occurs after therapy will be treated with washing the site with soap and water followed by topical application of Vaseline and tefla/gauze dressing.
- Skin hyperpigmentation or hypopigmentation: The site of laser application may heal with some post-treatment pigment changes. This adverse effect is more common in darker-skinned individuals, who will be excluded from this study for this reason. It may also occur following sun exposure. Subjects will be urged to wear sunscreen before and after treatment. Pigment alterations that do arise will generally fade in 3-6 months
- Scarring: A small chance of scarring exists. Rarely, hypertrophic scars or keloids may form in response to laser treatment. If this unusual complication should occur, intralesional triamcinolone acetonide in concentration of 10-40mg/mL at 4-6week intervals will be used to diminish the appearance.
- Skin infections: Cutaneous infection can occur with the use of laser therapy, although rare, and would require antibiotic treatment. In such circumstances, antibiotics will be given according to standard of treatment for cutaneous infection.
- Erythema/Purpura: Immediately post-laser, the treated skin is expected to become red and splotchy. This is followed by a purpuric response, where the affected area becomes purple or violaceous. This response

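### Section 9.2 classifies a tumour-free lesion above 90% of baseline size both as response and as non-response on the primary endpoint, and states no precedence

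*Combined protocol and SAP*

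**What the plan says.** Section 2.1 fixes the endpoint: "The primary endpoint is response, defined as CR or PR". Section 13.1 repeats it as the overall response rate. Section 9.2 then defines the categories twice.

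- **In words.** CR is either clinical and histological disappearance, or "Positive clinical assessment of the 'lesion' but negative histology". The second route has no size limit. Progression is "At least 10% increase in the size of the lesion on clinical evaluation". Stable disease is "Clinically, neither sufficient reduction to qualify for PR nor sufficient increase to qualify for PD". Neither of these last two mentions histology.
- **In a table**, introduced by "The following table summarizes the above response criteria". In the negative-histology row, CR is given for no lesion and for a lesion at 90% of baseline or less. The column "Lesion >90 but <110% baseline size" is given SD, and the column for 110% or more is given PD. Both of these entries carry a footnote: "not expected to occur".

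No sentence says whether the words or the table govern.

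Elsewhere, the note in section 4.0 says a subject in either arm with more than 10% growth is withdrawn and counts as a non-responder. Section 13.2 treats withdrawal for progression as non-response.

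**The concern.** The primary endpoint should give each lesion one category. Here a lesion with no tumour cells on excision, but with a visible mark close to its baseline size, is CR by one sentence of 9.2 and SD by another sentence and by the table.

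The footnote predicts how often this will happen. It does not settle the classification, because the cells still carry SD and PD. The plan's own content makes the situation plausible:

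- Temporary pigment change is listed as likely (7.1.12). On duration, 4.2 says: "Pigment alterations that do arise will generally fade in 3-6 months". The final assessment comes four weeks after the last session.
- The treated field includes 4 mm of normal skin (4.0, 7.1.7), so a residual mark need not be smaller than the baseline lesion.
- The diagnostic biopsy comes before enrolment (3.1.2, 5.1). A control whose tumour was largely removed by it could keep a mark of unchanged size.

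The trial is unblinded (3.3.3), so an open rule leaves a choice that could be made knowing the arm. With 15 and 5 evaluable subjects, a single choice can matter.

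**Working it through.** **Step 1. Compare the rules for negative histology with a visible lesion** (all from 9.2).

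| Size v baseline | Second CR route | Written SD/PD definitions | Table | Agreement |
|---|---|---|---|---|
| 90% or less | CR | neither applies | CR | yes: responder |
| above 90%, below 110% | CR | SD | SD* | no |
| 110% or more | CR | PD | PD* | no |

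The rules agree in one of the three cells and conflict in two. In both, the second CR route stands alone against the table and the written SD or PD definition. The fault is therefore also an overlap within the written definitions.

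**Step 2. Look for a tie-breaker elsewhere.** For growth above 10%, sections 4.0 and 13.2 give non-response without reference to histology, which supports PD. For lesions between 90% and 110%, no other section helps. Section 2.1 defines histological clearance as no tumour cells remaining in the post-treatment specimen, which fits CR, but it also says efficacy is measured clinically and histologically.

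**Step 3. How narrow is the size boundary?** Size is taken as the elliptical area in 9.1, so the ratio to baseline is (d1 × d2 at Day 84) / (d1 × d2 at baseline). For an assumed 10 mm × 10 mm lesion, one diameter falling by 1 mm gives 9 × 10 / 100 = 0.90, which the table calls CR. No change gives 1.00, which the table calls SD. One millimetre on a ruler separates response from non-response in a tumour-free subject.

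**Step 4. Effect on the planned test.** Inputs from 13.2: 15 treated, 5 control, one BCC each, one-sided Fisher, 0.05. With R responders in total and b among controls,

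p = Σ (x = 0 to b) C(R, x) · C(20 − R, 5 − x) / C(20, 5), where C(20, 5) = 15504.

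The plan's own rows reproduce:

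- 11 v 1: (56 + 840) / 15504 = 896 / 15504 = 0.0578 (plan 0.058)
- 12 v 1: (21 + 455) / 15504 = 476 / 15504 = 0.0307 (plan 0.031)
- 9 v 0: 462 / 15504 = 0.0298 (plan 0.030)

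Move one subject from the table's non-response to the CR of the second route:

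- Control: 12 v 1 becomes 12 v 2, (6 + 210 + 1820) / 15504 = 2036 / 15504 = 0.1313. Significance is lost.
- Control: 9 v 0 becomes 9 v 1, (252 + 2100) / 15504 = 2352 / 15504 = 0.1517. Significance is lost.
- Laser: 11 v 1 (0.0578) becomes 12 v 1 (0.0307). Significance is gained.

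Away from the borderline, the conclusion does not change:

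- Control: 14 v 1 (76 / 15504 = 0.0049) becomes 14 v 2, (16 + 480) / 15504 = 496 / 15504 = 0.0320. Still significant.

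**The case against.** **The authors set these cells aside, and the table can be read as their resolution of overlapping definitions.** This stands in part. The table does follow the written SD and PD definitions. But it is presented as a summary of the text, no precedence is stated, and it contradicts a CR route that the same text sets out separately.

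**Growth is non-response anyway.** This largely stands for 110% or more. Reclassifying that cell as CR would make the same growth a non-response at Day 56 and a complete response at Day 84. The boundary differs slightly: 4.0 speaks of more than 10% and 9.2 of at least 10%, so at exactly 110% only 9.2 applies.

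**Any misclassification matters at 15 v 5, and this is a pilot.** True. The p-values show sensitivity in selected rows and are not a forecast. They also apply only if every subject has one BCC; otherwise 13.3.2 moves to lesion-level rates and Donner's adjusted test.

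Three stronger readings are tempting, and the documents do not support them:

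- A reader might infer that the table makes every visible lesion with negative histology a non-response. It gives CR at 90% of baseline or less.
- A reader might infer that the table flatters the laser. It would do so if the affected subject were a control, and the reverse if the subject were in the laser arm. No net direction follows.
- A reader might infer that editing the two starred cells is enough. The size-only SD and PD definitions would still conflict with the second CR route.

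**Conclusion.** The point holds for negative histology with a lesion above 90% of baseline. Section 9.2 gives two incompatible answers on the primary endpoint there, with no rule to choose between them. The cell above 90% and below 110% is unresolved anywhere in the documents. The cell at 110% or more is contradictory within 9.2, but 4.0 and 13.2 point to non-response.

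One subject can move the planned test across 0.05 from the plan's own borderline rows: 0.031 to 0.131, or 0.058 to 0.031. It need not do so elsewhere (0.005 to 0.032 for 14 v 1 to 14 v 2). These figures assume one BCC per subject and full evaluable numbers. How often the cells will be occupied cannot be estimated: the documents give no rate of tumour clearance by diagnostic biopsy and no size distribution for residual marks. The case for correction rests on the endpoint needing one definition before data are seen, and on how little that costs.

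**What to change.** Before any outcome data are seen, make the words and table of 9.2 agree:

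1. Change the negative-histology cell above 90% and below 110% from SD to CR, in line with the second CR route and the definition of histological clearance in 2.1.
2. Add a positive-histology condition to the written SD definition.
3. Keep 110% or more as PD, a non-responder, whatever the histology, consistent with 4.0.
4. Limit the second CR route to lesions below 110% of baseline.
5. Delete the footnote and its asterisks.
6. If any subject falls in either cell, report the primary comparison under the alternative classification as a sensitivity analysis.

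After these edits each of the eight table cells has one category under both the words and the table. With positive histology: PR, PR, SD, PD. With negative histology: CR, CR, CR, PD.

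Letting the table govern the middle cell would also be consistent, provided the second CR route were limited to 90% or less. The version above is preferred because it keeps the written CR definition wherever no other section opposes it.

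The cost is one table cell, two short clauses, a footnote and one sentence in 13.3.2. No visit, measurement or sample size changes.

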## **3.0 PATIENT SELECTION**

### **3.1 Inclusion Criteria**

3.1.1 Adults age 18 years or older

3.1.2 Diagnostic biopsy must be no later than three months prior to enrollment

3.1.3 Lesion is biopsy-proven nodular or superficial BCC

3.1.4 BCC is 1.5 cm or less in diameter

3.1.5 BCC is on trunk or extremities

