## 4.0 TREATMENT PLAN

Subjects in the treatment arm will receive 3 treatments using the 595/1064 multiplex laser spaced by a four week interval (+/- 7 days), administered in an outpatient clinic setting. If a subject in the treatment arm has multiple BCCs satisfying inclusion criteria, all BCCs will be treated. The treatment settings for this laser will be as follows:

595 nm PDL at a fluence of 10 J/cm^2, a 10 ms pulse duration, and a 10 mm spot size, followed by 500 ms multiplex interpulse delay, followed by 1064 nm laser at a fluence of 40 J/cm^2, 10 ms pulse duration, and 10 mm spot size; the BCC lesion will be treated using 10% overlap with a single pass, along with 4 mm of normal skin. Dynamic cooling feature (cool air being blown onto treatment area) will be provided.

Subjects in the control arm will receive 3 regular study visits spaced 4 weeks (+/- 7 days) apart. If a subject in the control arm has multiple BCCs satisfying inclusion criteria, all BCCs will not be treated.

Four weeks (+/- 7 days) after the last (Day 84) both treatment and control patients will be assessed for final clinical appearance, measurement, and evaluation of the lesion by a dermatologist. Perpendicular diameters of the lesion will be measured with a ruler, as on initial evaluation, and surface area will be calculated. Residual tumor burden will be calculated based on change in surface area of the lesion.

Subjects will also undergo deep excisional biopsy encompassing the entire lesion to determine residual tumor cell presence. If histologic examination of the tissue reveals residual BCC, then the subject will receive standard of treatment.

A digital camera will be used to photograph the BCC immediately before, during and after treatment.

**Note:** If any clinical signs of progression are visible during this period (what we will consider greater than 10% growth), the subject in either treatment arm or control arm will be withdrawn from the study and undergo standard of care. Such a subject will be considered non-responder for the efficacy analysis.

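### The 10% area cut-offs for PR and PD lie close to ruler error on lesions of 15 mm or less, so unchanged lesions can be scored as response or progression

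*Combined protocol and SAP*

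**What the plan says.** Eligibility in 3.1.4 is "BCC is 1.5 cm or less in diameter", with no lower limit. Section 4.0 gives the method: "Perpendicular diameters of the lesion will be measured with a ruler, as on initial evaluation, and surface area will be calculated". Section 9.1 uses the ellipse formula on the two diameters and adds: "Residual tumor burden will be calculated by change in surface area of the lesion".

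Section 9.2 then sets two cut-offs at 10%. One route to PR is "At least 10% decrease in the size of lesion on clinical evaluation and positive histology or" complete clinical clearance with positive histology. PD is "At least 10% increase in the size of the lesion on clinical evaluation". PR counts fully in the main result, since 2.1 states: "The primary endpoint is response, defined as CR or PR".

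Lesions are measured at each visit (5.2), so an interim PD call can be made at Day 28 or Day 56. On a subject withdrawn for growth, 4.0 says: "Such a subject will be considered non-responder for the efficacy analysis". The study is unblinded (3.3.3). The only confirmation named in 9.3 is the biopsy. The text available gives no ruler graduation, repeat reading or allowance for measurement error.

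**The concern.** An area built from two short ruler readings is sensitive to small errors, and a 10% cut leaves little room for them. If reading error alone can move an unchanged lesion across the cut, some untreated stable lesions become responders and some stable lesions in either arm become permanent non-responders. The biopsy does not correct a false shrinkage: in the 9.2 table, positive histology with a lesion at 90% of baseline or less is PR. With 15 evaluable subjects against 5, one or two misclassified controls change what the laser arm must achieve.

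**Working it through.** **1. The plan's own figures.** One-sided Fisher tests on 15 v 5 give 0.0578 for 11 v 1, 0.0307 for 12 v 1 and 0.0298 for 9 v 0. The table in 13.2 (0.058, 0.031, 0.030) reproduces.

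**2. Area arithmetic.** With area = π(d1/2)(d2/2), the ratio to baseline is (d1′·d2′)/(d1·d2). For a round lesion of diameter d, a 1 mm shift on one diameter changes area by 1/d. A 1 mm shift on both changes it by (1 ± 1/d)² − 1.

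| Diameter | 1 mm on one diameter | 1 mm on both, same direction |
|---|---|---|
| 6 mm | ±16.7% | −30.6% / +36.1% |
| 8 mm | ±12.5% | −23.4% / +26.6% |
| 10 mm | ±10.0% | −19.0% / +21.0% |
| 12 mm | ±8.3% | −16.0% / +17.4% |
| 15 mm | ±6.7% | −12.9% / +13.8% |

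At 10 mm or less, 1 mm on one diameter reaches the cut. At 12 to 15 mm it does not; both diameters must be off in the same direction.

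**3. How often an unchanged lesion crosses.** This needs figures that the documents do not give. Assumptions: readings rounded to 1 mm; independent normal reading error on each diameter, SD 0.25, 0.5 or 1.0 mm; round lesions uniform on 5 to 15 mm; true size constant. False PR is a Day 84 area of 90% of baseline or less. False interim PD is growth above 10% at Day 28 or Day 56. Net false PR leaves out lesions already called PD. The duplicate rows use the mean of two readings of each diameter at baseline and at every visit, and call PD only when both readings at a visit exceed the cut.

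| Average over the size mix | SD 0.25 | SD 0.5 | SD 1.0 |
|---|---|---|---|
| False PR, single readings | 12% | 21% | 32% |
| False PR net of interim PD | 11% | 18% | 24% |
| False interim PD, single readings | 17% | 31% | 46% |
| False PR, duplicate readings | 4% | 11% | 25% |
| False interim PD, duplicate readings | 5% | 11% | 22% |
| False PR at a 50% area cut, single readings | 0.00% | 0.01% | 0.85% |

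These are averages over an assumed size mix, and single sizes vary more widely. At SD 0.5, false PR is about 32% at 6 mm and 9% at 15 mm.

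**4. Effect on 13.2.** One-sided Fisher thresholds for p<0.05:

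- 0/5 control responders: 9/15 needed in the laser arm (p=0.030)
- 1/5: 12/15 (p=0.031)
- 2/5: 14/15 (p=0.032)
- 3/5: not reached even at 15/15 (p=0.053)

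At a net false-PR rate of 18%, the chance of at least two control responders among five is 1 − 0.82⁵ − 5(0.18)(0.82⁴) = 1 − 0.371 − 0.407 = 22%. The same formula gives 10% at a rate of 11% and 35% at 24%.

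**The case against.** The strongest reply is that the rates are assumed. That stands: reading SD, graduation, independence of errors and size mix are all mine, and the mechanism is firmer than any percentage. With a 0.5 mm graduation, a one-step shift on both diameters reaches −10% only up to 0.5/(1 − √0.9) = 9.7 mm and +10% only up to 0.5/(√1.1 − 1) = 10.2 mm. A finer ruler does not remove the problem, though: at SD 0.5 mm, false PR over the same size mix is still about 17%.

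Second, the Schema and 4.0 speak of visible signs of progression and 11.1 of obvious progression, and photographs are taken at each visit. A clinician may not act on a single reading just over the cut, so the interim PD rates are upper figures for mechanical use of the rule. Silence on repeat readings is also not proof that none are taken; the visit source documents cited in Section 12.0 are not in the text available.

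Third, 9.1 computes area and then points to the criteria, so area is the natural meaning of size in 9.2. This largely stands. A one-line definition would settle it, because size reads as diameter in the eligibility criteria and a 10% change in both diameters is 19 to 21% of area (0.9² = 0.81; 1.1² = 1.21).

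Fourth, this is a small pilot, percentage change in lesion size is reported anyway (13.3.2), and ruler error does not affect histological clearance. All true, but the primary endpoint still counts PR with positive histology.

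**Conclusion.** The concern holds as a risk of misclassification: unchanged lesions can be scored PR or PD, most readily at 10 mm or less. The rates depend on the assumptions in the working, and the documents can neither confirm nor exclude them.

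A reader might infer three stronger things that the documents do not support:

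- That unchanged lesions will as a rule be misclassified. Rounding alone, with no reading error, misclassifies none, and the effect is much weaker at 12 to 15 mm.
- That the scenarios in 13.2 are invalid. They are labelled hypothetical, two of the three already allow one control responder, and 0 or 1 remains the likelier outcome at the net rates above. They are weakened, because two control responders become a realistic possibility that the table does not show.
- That a 50% cut is required. Nothing in the documents fixes that figure; it is one option among several.

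This should be fixed, as a cheap improvement. It does not undermine the trial.

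**What to change.** 1. In 9.2, state that size means the surface area from 9.1.
2. For endpoint scoring, use the mean of two readings of each diameter at baseline and at every visit, by the same dermatologist. Score PD only when both readings at that visit exceed the cut. On the assumptions above this roughly halves false PR at SD 0.5, but helps less at SD 1.0.
3. Because error remains, set the size cut for PR with positive histology above the duplicate-reading error. The sponsor should choose and justify it; a 50% area decrease is one candidate. At the least, report response at a stricter cut as a sensitivity analysis. Keep lesions at 90% of baseline or less with negative histology as CR. Otherwise a new cut applied to the whole 9.2 table would turn some histological clearances into SD.
4. State in 13.2 how a subject withdrawn for growth but not confirmed as PD is counted. As written, withdrawal for PD is a non-response and any other withdrawal is non-evaluable, so such a subject could drop out of the analysis.

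When a patient leaves the study for care remains a clinical decision. The growth rule is worded differently in the Schema and 4.0 (more than 10%), 9.2 (at least 10%) and 11.1 (a 10% increase), and these must be reconciled. A reading of 10 mm then 11 mm on one diameter is exactly +10.0%.

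Cost: protocol wording and a second ruler reading at each visit. If the PR cut is raised, small true shrinkages no longer count and the response rate may fall.
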